### **STUDY DESIGN**

This is a double-blind randomized placebo-controlled trial, studying zinc supplementation to prevent HIV comorbidities that are linked to inflammation in subjects  $\geq 18$  years old HIV-infected patients, on stable ART (for at least 12 weeks) and with zinc levels  $\leq 0.75$  mg/L in the last 60 days. The duration of the study will be 24 weeks. The total sample size is 95 patients (n=62 on active and 31 on placebo). Patients will be randomized 2:1 to zinc gluconate tablets at a dose of 90 mg elemental zinc daily or matching placebo. For this confirmatory phase of the randomized trial, we propose twice the number of subjects in the treatment arm compared to the placebo arm from the context of feasibility, resource allocation or logistics, ethical point of view, and risk-benefit ratio. We propose to measure a number of inflammatory and immune activation biomarkers. From our prior experiences with these biomarker distributions, we may find more variability (may include outliers) in some of the response variables (biomarkers) in the treatment arm than the variability in the response variables in the placebo arm. To reduce the impact of such variability in estimating the effect sizes, having more subjects in the treatment arm should lead to more precise estimates, and hence more powerful statistical inferences. Study drugs will be provided free of charge to study participants for the duration of their participation in the study. Antiretroviral therapy will not be provided by the study. The decision for ART changes or discontinuation will be left to the primary care provider, but these changes will be documented in the study chart and will be taken into account during the analyses.

Subjects will be evaluated and data will be collected according to the following schedule:

Evaluation (Weeks)	Screen I	Screen II	Entry	6	12	18	24
Family history of CVD and diabetes		X					X
Framingham and Reynolds Risk Scores			X		X		X
Targeted physical, blood pressure, weight		X	X	X	X	X	X
Anthropometric Measurements	X	X					X
Compliance, safety monitoring				X	X	X	
Smoking, illicit drugs and alcohol status	X				X		X
Dietary and Activity status	X				X		X
Height	X						
Hematology/chemistries	X	X	X	X	X	X	X
Urine $\beta$ -HCG (women)	X	X	X	X	X	X	X
Lipoprotein profile			X		X		X

Insulin, glucose, HOMA-IR			X	X		X
Inflammation and immune activation markers			X	X		X
Gut integrity, microbial translocation, intestinal permeability			X	X		X
Oxidative markers			X	X		X
Zinc level	X		X	X		X
Copper level			X			X
EndoPat, AGE testing		X		X		X
Resting Energy Expenditure (REE)		X				X
Cognivue			X			X
Stored plasma, serum and urine		X	X	X	X	X
Stored PBMC			X	X		X
Stored Stool		X	X	X		X

\*\*\* Plasma, serum, urine and stool will be stored in the local laboratory in a -70 degrees freezer for potential future metabolic, cardiovascular, oxidative markers, inflammation markers, and nutrition markers. Urine will be used for possible oxidative and bone markers.

#### Randomization:

The randomization schedule will be performed by a statistician using SAS software to create a list based on permuted variably sized block randomization with block sizes of 6 to generate 50 allocated numbers in two arms. The randomization schedule will be generated by the statisticians prior to the start of the trial by and provided to the investigational pharmacy. After being provided to the pharmacists, the randomization schedule will be maintained in a locked, secured location at the pharmacy. Only site pharmacists can access the randomization schedule at the time of the intervention assignment.

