**Sample size and population:**

The total sample size is 95 patients, 63 patients will be randomized to two 45 mg (or 90 mg) capsules of zinc gluconate and 32 patients will receive two matching capsules of placebo drug. This study will be conducted at the University Hospitals Cleveland Medical Center. Recruitment will be done at the Special Immunology Unit (SIU) at the University Hospitals Main Campus.

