### **DETAILED STUDY PROCEDURES BY VISITS**

**Screening I/II:** Before they enter, patients will be asked to visit the clinic at least once to be screened and ensure that they meet the requirements for entry into the study. Screening may take place on the same day as a normally scheduled clinic appointment, as long as subject is fasting. Before any tests can be obtained as part of this study, patients would have to decide whether or not they would like to participate in this study.

- If they choose to enroll, the informed consent form will be signed. The site investigator or a member of the study team will conduct the consenting process and a checklist indicating date and time the consent was signed, who was present, version date and if a copy was provided to participant will be filed in the subjects chart
- A targeted physical examination will be performed including height, weight and blood pressure
- Recent blood work will be reviewed to be sure that they meet the inclusion criteria. The HIV-1 RNA, and HIV testing to confirm HIV status will be obtained from the clinical chart as these are a part of routine care.
- Blood will be drawn for hematology/chemistries and zinc
- Plasma, serum, urine and stool will be collected and stored for potential future testing.
- For woman of reproductive potential, a urine sample will be taken for a pregnancy test.

If a participant does not meet inclusion criteria it will be noted in the chart with the reason for ineligibility.

If a participant meets the inclusion criteria and chooses to enroll, randomization will occur at the entry visit. The study team will notify the pharmacist who will allocate them to one of the two interventions according to the randomization schedule. Participants should start the intervention within two days of randomization allocation.

**Study Entry:** For entry visit, this will be fasting, as defined by no food or drink, except for plain water and medications for at least 8 hours. The following procedures will be done at entry.

- A medical history including family history
- Targeted physical exam including weight and blood pressure
- Patients will fill out a dietary, physical activity, and a substance questionnaire.

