### **STATISTICAL CONSIDERATIONS:**

Primary goal of this study is to assess the benefit of zinc supplementation by increasing zinc levels and hence improving several important biomarkers. To assess the effect of supplementation and its' positive influence on markers of inflammation and immune activation known to be associated with HIV-comorbidities, 95 HIV+ subjects (see below for the sample

size justification) will be studied for 6 months from the available HIV+ subjects pool. During this period outcome variables (primarily, zinc levels and sCD14) and biomarkers will be measured at baseline (0), 6, 12, 18, and 24 weeks. The outcome variables will be analyzed, and predicted values will be portrayed longitudinally. The main outcome variables zinc levels and sCD14 are continuous variables. Therefore, linear mixed model and likelihood ratio test will be used in testing hypotheses (see details below).

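### The pre-trial randomisation list holds 50 allocations for a trial of 95, and the stated arm sizes do not add up consistently (62 + 31 = 93 in one place, 63 + 32 = 95 in another)

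*Combined protocol and SAP*

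**What the plan says.** **Randomization section.** The list is to use "permuted variably sized block randomization with block sizes of 6 to generate 50 allocated numbers in two arms". On timing: "The randomization schedule will be generated by the statisticians prior to the start of the trial". The list then goes to the investigational pharmacy and is kept locked there. The section does not repeat the allocation ratio.

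**Detailed Study Procedures by Visits, Screening I/II.** At the entry visit the study team notifies the pharmacist, "who will allocate them to one of the two interventions according to the randomization schedule". No other source of allocations is mentioned.

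**Planned size and ratio.**
- Study Design: "The total sample size is 95 patients (n=62 on active and 31 on placebo"), and "Patients will be randomized 2:1 to zinc gluconate tablets".
- Précis, Sample size and population: "The total sample size is 95 patients, 63 patients will be randomized to two" zinc capsules, and "32 patients will receive two matching capsules of placebo drug".
- Statistical Considerations, opening paragraph: "95 HIV+ subjects (see below for the sample" size justification). The mixed model under Aim 1&2 also indexes subjects from 1 to 95.
- Sample Size and Power analysis: 27 control and 54 intervention participants before losses, raised for 15% missing or non-compliant to final figures of 31 and 62.

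**The concern.** A pre-generated list has to be at least as long as the number of people to be randomised from it. Here it is roughly half as long. Followed literally, the schedule runs out with 45 participants still to be enrolled, and the protocol does not say who produces the remaining allocations, at what ratio, or in what block sizes.

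An extension improvised during the trial could weaken concealment or disturb the ratio. That is a possible consequence and not a demonstrated one. The plain defect is that an operative instruction cannot deliver the planned trial.

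The arm sizes are a separate, smaller matter. The statistician and pharmacy are given two targets, and the total of 95 is referred to a justification that ends at 93.

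**Working it through.** **1. List length against sample size**

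| Target | Allocations on list | Shortfall | Share of target |
|---|---|---|---|
| 95 | 50 | 95 − 50 = 45 | 45/95 = 47.4% |
| 93 | 50 | 93 − 50 = 43 | 43/93 = 46.2% |

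If 50 meant 50 per arm, the list would be 1:1. Study Design specifies 2:1, and the active arm would still be short (50 against 62 or 63).

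**2. Block structure**

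At 2:1, a block of 6 holds 4 active and 2 placebo. 50/6 = 8.33, so the list is 8 full blocks (48 allocations, 32:16) plus 2 from a ninth. It would therefore be 34:16, 33:17 or 32:18. Ending mid-block is not an error in itself, but it shows that 50 was not derived from the block design. The sentence also calls the blocks variable in size while giving only one size.

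The shortest list of complete blocks that covers either 93 or 95 is 16 × 6 = 96, which is 64:32.

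**3. Arm sizes**

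- Study Design and the power section: 62 + 31 = 93.
- Précis: 63 + 32 = 95.

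The two sets correspond to two ways of allowing for 15% loss from 54 and 27:

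| | × 1.15 | ÷ 0.85 |
|---|---|---|
| Intervention 54 | 62.1 | 63.5 |
| Control 27 | 31.05 | 31.8 |
| Total 81 | 93.15 | 95.3 |

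Multiplying by 1.15 gives 62/31. Dividing by 0.85, which is the step that leaves 81 after a 15% loss, gives about 95. It appears that the total followed one calculation and the Study Design arm sizes the other.

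**4. Effect of 93 versus 95 on power**

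Inputs from Sample Size and Power analysis: SD 0.32, correlation 0.85, difference 0.08 in log(sCD14) change, level 0.10, power 80%, ratio 2:1.

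For the change method with r post-baseline measurements, SD of change = 0.32 × √[(1 + (r − 1) × 0.85)/r − 2 × 0.85 + 1].

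With r = 5 this is 0.32 × √0.18 = 0.1358. Control-arm size = 1.5 × [0.1358 × (1.645 + 0.842)/0.08]² = 26.7, hence 27 control and 54 intervention. This reproduces the plan's figures. It needs a two-sided level of 0.10 and five post-baseline measurements, whereas Statistical Considerations specifies one-sided tests; I use this variant because it is the one that returns 54/27.

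Power by noncentral t:

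| Evaluable (intervention/control) | Two-sided 0.10, r = 5 | One-sided 0.10, r = 5 |
|---|---|---|
| 54/27 | 0.798 | 0.886 |
| 62/31 less 15% = 52.7/26.35 | 0.789 | 0.880 |
| 63/32 less 15% = 53.55/27.2 | 0.798 | 0.886 |

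With one post-baseline measurement, one-sided, the change from 54/27 to 52.7/26.35 is 0.740 to 0.733. Across 1, 2, 4 or 5 post-baseline measurements, one- or two-sided, the loss is 0.01 or less.

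**The case against.** The best defence is that 50 is leftover text. The revision summary says the document was updated to include the R33 phase, the objectives refer to an earlier R21, and Study Design calls this the confirmatory phase. A list of 50 may belong to the earlier phase, and a correct list may already exist. That is plausible, but the documents do not say so. The sentence stands in the current operative section and would need correcting even so. What survives of this defence is that the 47% describes the protocol as written; it is not evidence of how allocation was actually done.

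The safeguards also count. A statistician generates the list, only site pharmacists can see it, and participants, staff and the statistician are blinded. Producing further blocks is simple, and no bias or loss of power has been shown. I accept that, and it limits the severity.

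The 2:1 ratio is given in Study Design, so its absence from the Randomization section is a matter of convenience. The two-participant difference in totals is clerical.

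**Conclusion.** The concern holds and should be fixed. As written, the schedule covers 50 of 95 planned participants, leaving 45 (47%) without a pre-generated allocation, or 43 of 93 (46%) on the smaller total. No reading of the text removes the gap. This rests on the absence of any second list or extension rule in the documents.

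The arm-size conflict is a plain addition error in Study Design (62 + 31 is 93, not 95), set against 63 + 32 in the Précis. Its effect on power is negligible. Neither point shows that allocation was biased or unblinded.

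**What to change.** **Randomization section.** Describe one list, generated before enrolment, that covers the full sample at 2:1, for example 16 blocks of 6 giving 96 slots (64:32). Either drop the reference to varying block size or state the sizes used. A 96-slot list does not require a target of 96: stopping at 95 gives 63:32 (probability 2/3) or 64:31 (probability 1/3), depending on which allocation is left unused. If a longer list already exists, report its actual length, ratio and block sizes instead.

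**Sample-size figures.** Use one total and one pair of arm sizes.
- If the total stays at 95, give 63:32 as the target in Study Design and in Sample Size and Power analysis, and show the 15% allowance as division by 0.85. The Précis, the opening of Statistical Considerations and Aim 1&2 then need no change.
- If the total becomes 96 (64:32), all five places need the new figures.

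**Cost.** One rewritten sentence in the Randomization section and a few aligned numbers. Keeping 95 adds no procedure and no participants; choosing 96 adds one.

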#### Blinding:

Patients, study staff, and the study statistician will be blinded to treatment allocation (zinc gluconate or placebo capsules).

The research staff as well as the principle investigator will remain blinded to treatment assignment. The research staff will be responsible to prepare DSMP reports with the principal investigator and will include enrollment and dropout rates, protocol deviations, subjects symptoms, review of clinical, laboratory results and percent adherence to treatment, while remaining blinded to treatment allocation.

The principle investigator, as well as the DSMB board will remain blinded throughout the conduct of the clinical trial unless unblinding is warranted to optimize management of an adverse event or for other safety reasons. This will occur in a private location to ensure the rest of the team remains blinded.

All statistical analyses will also be done in a blinded fashion. Data will be exported to the statistician as arm A versus arm B by the research nurse to preserve blinding. For analyzing adherence, they will also only have access to the percent as opposed to pill counts the research nurse uses to calculate this.

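### The randomisation section promises variable block sizes but gives one size, 6, in the protocol itself, and its list of 50 numbers does not cover 95 patients

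*Combined protocol and SAP*

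**What the plan says.** The Randomization section describes "permuted variably sized block randomization with block sizes of 6", and has this scheme produce a list of 50 numbers across the two arms. The STUDY DESIGN section sets the ratio: "Patients will be randomized 2:1".

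The planned size is 95 in two places, with different splits. STUDY DESIGN has "The total sample size is 95 patients (n=62 on active and 31 on placebo", which adds to 93. The précis, under Sample size and population, has "The total sample size is 95 patients, 63 patients will be randomized to two 45 mg (or 90 mg) capsules", with 32 on placebo, which adds to 95.

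Concealment rests on the pharmacy: "Only site pharmacists can access the randomization schedule at the time of the intervention assignment". The Blinding section blinds patients, study staff, the investigator, the statistician and the DSMB.

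Two passages bear on whether earlier allocations could be inferred. The text under Week 12 and 24 says that the number of pills dispensed follows the randomised arm, and has the study team count what is returned. The précis gives two capsules in each arm.

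**The concern.** Block sizes are varied at random so that nobody can tell where a block ends. With one known size, the remaining places in a block are determined once either arm's places are used up. A person who could infer earlier allocations could then time an entry visit to suit a patient. The plan leaves room for this: entry may fall up to 30 days after screening, and all enrolment at the single site draws on one list. The size is also printed in the protocol that site staff hold.

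Separately, a list of 50 cannot allocate 95 patients, so the sentence does not fully describe the list this trial needs.

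**Working it through.** **Inputs.** Block size 6 and list length 50 (Randomization); ratio 2:1 (STUDY DESIGN); N = 95 (précis and STUDY DESIGN). The plan states no predictability figure, so there is none to reproduce. Its arm sizes confirm the ratio: 54/27 = 2 before dropout and 62/31 = 2 after.

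**List length.** 95 − 50 = 45 patients have no number. 50 = 8 × 6 + 2, so the list is not a whole number of blocks of 6. Nor is 95 (15 × 6 + 5).

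**Certain allocations, fixed block of 6.** Each block holds 4 zinc and 2 placebo, in one of 15 orderings. To someone who knows the size and all earlier allocations, an allocation is certain when every remaining place belongs to one arm. The number of certain allocations is therefore the length of the block's final single-arm run.

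| Final run | Orderings |
|---|---|
| 1 | 8 |
| 2 | 4 |
| 3 | 2 |
| 4 | 1 |

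Mean = (8×1 + 4×2 + 2×3 + 1×4)/15 = 26/15 = 1.733 per block, and 1.733/6 = 28.9%. The closed form agrees: 4/(2+1) + 2/(4+1) = 1.333 + 0.400 = 1.733.

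For N = 95 the last block is cut at 5, so the expected count is 15 × 26/15 + (26/15 − 1) = 26.73, and 26.73/95 = 28.1%. Simulation gave a mean of 28.2% with a 95% range of 21% to 37%.

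**Best guess.** Let f(x, y) be the expected number of correct guesses with x zinc and y placebo places left:

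f(x, y) = max(x, y)/(x+y) + [x/(x+y)] f(x−1, y) + [y/(x+y)] f(x, y−1)

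This gives f(3,2) = 3.6 and f(4,1) = 4.2. Then f(4,2) = 0.667 + 0.667×3.6 + 0.333×4.2 = 4.467, and 4.467/6 = 74.4%. Always guessing zinc gives 4/6 = 66.7%. The difference of 7.8 percentage points is about 7 patients in 95.

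**Variable sizes.** The documents give no alternative sizes, so the sets below are my assumptions. In the simulations each size is equally likely, and the observer knows the set of sizes and every earlier allocation. Ranges reflect separate runs, with lists of 93 or 95.

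| Sizes | Certain | Best guess |
|---|---|---|
| 6 only | 28–29% | 74% |
| 3, 6 | 10% | not computed |
| 6, 9 | about 5% | not computed |
| 3, 6, 9 | 3–4% | not computed |
| 6, 9, 12 | 2.3% | 72% |

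**Route to earlier allocations.** If pill numbers differ by arm, the team that counts returns could learn the arm from the counts. If both arms receive two capsules, it could not. The text under Week 12 and 24 points to the first and the précis to the second. The Blinding section gives the statistician adherence percentages rather than pill counts, but leaves the counts with the research nurse.

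**The case against.** The strongest answer is the blind. All of the predictability figures require knowledge of earlier allocations, and the plan provides a locked pharmacy list and double blinding. That stands: with the blind intact, the gain from knowing the block size is near zero.

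The sentence on pill numbers may also be loose wording for the pharmacy dispensing the assigned product. That is possible, which is why the passages need reconciling and why the text does not show a breach.

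The wording is ambiguous too. It uses a plural, so a list of sizes may be incomplete, and with 50 numbers it may not describe the list for this phase at all. The documents do not show how the list was actually built. They show only that the scheme as written has one size.

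Two stronger readings are tempting and unsupported:

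- From "Data will be exported to the statistician as arm A versus arm B by the research nurse to preserve blinding" a reader might infer that the enrolling team can see the pattern of allocations. The Blinding section does not say when the export happens, or that this nurse screens or enrols. The stored inflammation markers are batched to the end of the study, and an export after enrolment closes cannot help anyone predict.
- A reader might take 29% as a ceiling. It is an average. Within a block the share runs from 1/6 (17%) to 4/6 (67%), and about 42% of simulated lists of 95 exceeded 29%.

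Finally, the gain from varying the sizes is mostly the loss of certainty. Overall guessing accuracy barely moves.

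**Conclusion.** The point holds as a fault in the specification with a small practical risk. The Randomization section claims variable sizing and describes a fixed block of 6, and its list is 45 numbers short of the planned sample. If the blind holds, the consequence for bias is negligible. If it failed completely, about 29% of allocations on average would be certain. This rests on 2:1 blocks of 4 and 2, a known size and full knowledge of earlier allocations. Nothing in the documents shows that allocation concealment was or will be broken. The conflict over pill numbers is the one documented route by which earlier arms might be inferred, and it remains open until those passages agree.

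**What to change.** 1. Rewrite the Randomization section so that the list covers the planned sample (after settling 93 against 95) and uses at least two block sizes that are multiples of 3, drawn in random order. Sizes 6 and 9, or 6, 9 and 12, would serve as examples.
2. Hold the sizes only with the statistician who generates the list and the pharmacy, and take them out of the protocol. State there only that sizes vary and are withheld from site staff.
3. Reconcile the text on pill numbers under Week 12 and 24 with the capsule numbers in the précis.
4. If a list is already in use, apply the change to the remaining allocations and report the sizes actually used.

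**Cost.** Generating such a list takes no extra effort. Stopping mid-block can leave the arms slightly further from 2:1. The worst case is 4 − 4×2/3 = 1.3 patients with a block of 6, 6 − 6×2/3 = 2 with 9, and 8 − 8×2/3 = 2.7 with 12. The text change is a protocol modification and needs IRB review.

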#### Blinding:

Patients, study staff, and the study statistician will be blinded to treatment allocation (zinc gluconate or placebo capsules).

The research staff as well as the principle investigator will remain blinded to treatment assignment. The research staff will be responsible to prepare DSMP reports with the principal investigator and will include enrollment and dropout rates, protocol deviations, subjects symptoms, review of clinical, laboratory results and percent adherence to treatment, while remaining blinded to treatment allocation.

The principle investigator, as well as the DSMB board will remain blinded throughout the conduct of the clinical trial unless unblinding is warranted to optimize management of an adverse event or for other safety reasons. This will occur in a private location to ensure the rest of the team remains blinded.

All statistical analyses will also be done in a blinded fashion. Data will be exported to the statistician as arm A versus arm B by the research nurse to preserve blinding. For analyzing adherence, they will also only have access to the percent as opposed to pill counts the research nurse uses to calculate this.

